#### **5.5.2 Prohibited concomitant therapy**

Concomitant use other anti-cancer therapies, including radiation, or other investigational agents is not permitted while subjects are receiving study drug during the treatment phase of the study. Corticosteroids may be administered for treatment of a tumor flare reaction as detailed above.

### **5.6 Duration of Therapy and Criteria for Removal From Study**

- Treatment will continue until the occurrence of any of the following events.
- Disease progression (excluding tumor flare)
- Adverse event(s) that, in the judgment of the Investigator, may cause severe or permanent harm or which rule out continuation of the treatment regimen.
- Discontinuation of thalidomide or lenalidomide for any reason. (Note, patients who are unable to tolerate rituximab infusions may still continue on the protocol.)
- Major violation of the study protocol.
- Withdrawal of consent
- Lost to follow up
- Death
- Suspected pregnancy or positive pregnancy

### **5.7 Duration of Follow Up**

Subjects who discontinue treatment for any reason will be followed for 30 days. At 28 days post treatment, subjects will undergo a safety assessment. In addition, off study evaluations per the Schedule of Assessments, Section 10 will be done.

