## 2.4 Overview of CLL

Chronic lymphocytic leukemia (CLL) is the most common leukemia in North America, with an estimated 15,000 new cases diagnosed in the United States in 2007 [12]. CLL is typically a disease of advanced age, with a median age at diagnosis of approximately 65 years, and a male-to-female ratio of 2:1 [13]. CLL is characterized by the clonal expansion of long-lived, mature B lymphocytes that co-express the CD5, CD19, and CD23 surface antigens [14-15]. The malignant cells of CLL are frozen in the G0 stage of the cell cycle, increasing in numbers due more to a lack of apoptosis than augmented proliferation [16-21]. The morbidity and mortality associated with CLL results primarily from the progressive accumulation of lymphocytes in secondary lymphoid tissues and bone marrow. Patients might remain asymptomatic for prolonged periods of time, but most develop disease progression, with 70% of CLL patients dying from causes related to their disease [22].

Overall, patients with CLL have a median life expectancy of almost nine years, but great variability exists depending upon several well described prognostic markers [23]. Traditional prognostic markers include stage [24-25], age [26], gender [26], pattern of bone marrow involvement [27-28], lymphocyte doubling time [29-30], number of circulating prolymphocytes [31-32], and beta-2-microglobulin level [33-34]. More recently, prognostic markers have been identified that are based more on the biological features of the malignant lymphocytes themselves. These novel prognostic markers include: IgVH mutational status [35-36], CD38 expression [36], zap-70 expression [37], and interphase FISH (iFISH) abnormalities [38].

Criteria initially described by the National Cancer Institute Working Group (NCI-WG) on CLL [14], and updated by the International Workshop on CLL (IWCLL) [15], describe the indications for initiation of therapy for patients with CLL as: evidence of progressive marrow failure as evidence by anemia or thrombocytopenia (Rai stage III or IV), massive or symptomatic splenomegaly, massive or symptomatic lymphadenopathy, progressive lymphocytosis with an increase of more than 50% over a 2-month period or a lymphocyte doubling time of less than 6 months, autoimmune cytopenias poorly responsive to corticosteroids, or the presence of B symptoms (fevers greater than 38.0, unintentional weight loss >10% in six months, significant fatigue, or night sweats) [15].

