### 5.3 Visit schedule and assessments

Screening Assessments and all on study scheduled visits and assessments are outlined in Section 10 Table of Study Assessments.

At treatment discontinuation, subjects will undergo off study evaluations per the Schedule of Assessments, Section 10. In addition, a safety assessment will be done approximately 28 days post the last dose of study drug. Follow-Up contact with the subjects should occur at a minimum of sixth months.

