CT of the chest / abdomen / pelvis 						
Hematology 	X	X	X	X	X	X
Serum chemistries 	X	X	X	X	X	X
Pregnancy testing 	X 				X 	
T-cell Repertoire Studies 	X 					
Comply with RevAssist® and S.T.E.P.S.® program	X					
Response assessment 	X					
Record adverse events 	X		X			X
Perform drug accountability	X					
Prescribe and dispense study drugs for next cycle 	X					

An unscheduled visit can occur at any time during the study. Source must be maintained for these unscheduled visits. The date for the visit and any data generated must be recorded on the appropriate CRF. Source documents for these unscheduled visits must also be maintained.

Procedure	Rituximab administration Cycles 7, 13, and 19				For all other cycles 8 and beyond 	Discontinuation From Protocol therapy
	Day 1	Day 8	Day 15	Day 22	Day 1	
Medical history assessment	X				X	
Interim history	X	X	X	X	X	
Physical examination, vital signs, weight	X	X	X	X	X	X
ECOG performance status	X	X	X	X	X	X
Lymph node, spleen and liver assessment by physical exam 	X	X	X	X	X	
Bone marrow assessment 						
BlyS/BAFF Analysis 	X				X 	
Peripheral Blood Cell Subset Analysis 					X 	
CD4/CD8/CD56 cell count						X
CT of the chest / abdomen / pelvis 	X				X 	X
Hematology 	X	X	X	X	X	X
Serum chemistries 	X	X	X	X	X	X
Pregnancy testing 	X 		X 		X 	X 
Comply with RevAssist® and S.T.E.P.S.® program	X				X	
T-cell Repertoire Studies 					X 	
IFE, beta-2-microglobulin, DAT	X				X 	
Response assessment 	X				X 	X
Record adverse events 	X	X	X	X	X	X 
Perform drug accountability	X				X	
Prescribe and dispense study drugs for next cycle 	X				X 	
Rituximab administration	X 	X 	X 	X 		
MRD status – peripheral blood assessment	X				X 	
Obtain Follow-Up anti-cancer treatments						F/u phase : Q 3 months
Obtain Follow-Up survival information						F/u phase : Q 3 months

 ≤ 28 days from baseline (First day study drug administration)

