### 13.3 Statistical Methodology

Primary Endpoint:

- The primary endpoint of response rate (overall, CR, PR) will be estimated and a 95% confidence interval will be estimated via binomial proportions

Secondary Endpoints:

- With adequate follow-up time, progression-free survival (PFS) will be assessed by Kaplan-Meier survival analysis and 95% confidence intervals will be calculated using Greenwood's formulae. PFS will be defined as the time from the first treatment day until objective or symptomatic progression (or until date of last follow-up if no progression).
- Duration of Response: from the end of the last treatment until evidence of progressive disease.
- Time to Response
- Overall Survival
- The frequency of subjects experiencing toxicities will be tabulated. Toxicities will be assessed and graded according to CTCAE v4.0 terminology. Exact 95% confidence intervals around the toxicity proportions will be calculated to assess the precision of the obtained estimates.

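### Post-treatment follow-up is stated in three ways that do not agree, and no disease assessment is clearly scheduled after a stop without progression, which weakens duration of response and PFS

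*Combined protocol and SAP*

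**What the plan says.** Three places describe what happens after treatment stops.

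- Section 5.7: "Subjects who discontinue treatment for any reason will be followed for 30 days", with a safety assessment at 28 days. It then adds: "In addition, off study evaluations per the Schedule of Assessments, Section 10 will be done".
- Section 5.3: "Follow-Up contact with the subjects should occur at a minimum of sixth months". It is unclear whether this is an interval or a total duration. The same section places the off-study evaluations at treatment discontinuation.
- Section 10 calendar, discontinuation column: the rows for later anti-cancer treatment and for survival ("Obtain Follow-Up survival information") both carry "F/u phase : Q 3 months". No end date is given.

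Those two rows are the only ones assigned to the follow-up phase. In the same column, physical examination, blood counts, CT and response assessment are each marked once. Footnote 12 sets CT at six-monthly intervals for three years and yearly after that, without saying whether this continues off treatment.

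Section 5.6 ends treatment for several reasons other than progression, including "Discontinuation of thalidomide or lenalidomide for any reason". Sections 11.7 and 13.3 start duration of response at the end of the last treatment and end it at progression. Section 13.3 runs PFS to progression, "or until date of last follow-up if no progression", and analyses it by Kaplan-Meier. OS has a definition in Section 11.7 but no stated method or censoring rule.

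**The concern.** OS, PFS and duration of response are all secondary objectives, and all three need information from after treatment stops. Two separate problems arise.

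First, the length and frequency of follow-up depend on which sentence a site follows. Section 2.4 says that "patients with CLL have a median life expectancy of almost nine years", so 30 days of contact would say little about survival.

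Second, harmonising the intervals alone would not be enough. The calendar is the fullest of the three statements, yet its follow-up phase asks whether the patient is alive and whether new therapy has begun. It does not ask whether the disease has progressed. A patient who stops in remission therefore contributes little to PFS after the stop and may have no reliable end date for duration of response. Missed progression dates may not be recoverable later.

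**Working it through.** **1. The plan's own design figure.** The probability of a positive result is the sum over x = 7 to 11 of P(Bin(11, p) = x) × P(Bin(13, p) ≥ 18 − x). At p = 0.60 this is 0.0930 (early-stop probability 0.467). At p = 0.80 it is 0.8015 (early-stop probability 0.050). The stated 10% level and 80% power in Section 13.1 reproduce. This test does not use post-treatment follow-up.

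**2. The follow-up statements side by side.**

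| Source | Contact after stopping | Disease assessment after the discontinuation visit |
|---|---|---|
| 5.7 | 30 days, plus Section 10 off-study evaluations | None stated |
| 5.3 | Minimum of six months, meaning unclear | None stated |
| Section 10 | Every 3 months, no end date | None assigned; footnote 12 unclear for CT |

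**3. Duration of response.** Treatment continues to progression or unacceptable toxicity (Section 5.2). For a responder who stops because of progression, the interval from last treatment to progression is about zero by construction. The endpoint is therefore informative only for responders who stop without progression, and for them it lies wholly in the period with no clearly scheduled assessment.

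**4. PFS, illustrated.** The documents give no progression or stopping rates, so every input here is assumed: exponential times, median PFS on treatment of 24 or 36 months, and 20% or 40% stopping without progression by 12 months. PFS is censored at the stop.

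Let S be 24-month PFS at the on-treatment hazard, and q the probability of no such stop by 24 months. Then S = 0.5^(24/24) = 0.500 or 0.5^(24/36) = 0.630, and q = 0.8² = 0.64 or 0.6² = 0.36.

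Kaplan-Meier censored at the stop estimates S. If the hazard is unchanged after stopping, true PFS is also S, so there is no bias. If the hazard doubles after stopping:

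true PFS = S × [q + (−ln q)(q − S) / ln(q/S)]

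For S = 0.500 and q = 0.64: 0.500 × [0.64 + 0.4463 × 0.14 / 0.2469] = 0.447.

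| Median PFS | Stopped by 12 months | Estimated | True, hazard doubled | Overstatement |
|---|---|---|---|---|
| 24 mo | 20% | 0.500 | 0.447 | 5 points |
| 24 mo | 40% | 0.500 | 0.398 | 10 points |
| 36 mo | 20% | 0.630 | 0.582 | 5 points |
| 36 mo | 40% | 0.630 | 0.537 | 9 points |

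A simulation of 200,000 patients per scenario agrees to within 0.002.

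**5. OS, by which sentence governs.** Further assumptions: median survival after progression of 36 months, no deaths before progression, and data cut-off at 60 months. With the hazard unchanged after stopping, true 36-month OS is 3 × 0.5 − 2 × 2^(−1.5) = 0.793 for median PFS of 24 months, and (1 + ln 2) × 0.5 = 0.847 for 36 months. Over all simulated scenarios, including a doubled hazard, the true value is 0.76–0.85.

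- Calendar governs: survival contact continues and the true curve is recovered.
- 30-day sentence applied literally: the estimate is 0.98–0.99, with about 0.1–0.3 deaths captured in 24 patients against 7.7–11.5 with continued contact.

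**The case against.** **A reader might infer that survival follow-up ends at day 30 and that OS cannot be estimated.** The documents do not support that. Section 5.7's last sentence and Section 5.3 both send stopped patients to Section 10, whose discontinuation column holds the 3-monthly survival contact. The 30 days sit beside the 28-day safety visit and read naturally as a safety window. Six months, read as a minimum frequency, is met by contact every 3 months. All of this stands. What remains is that Section 5.3 places the off-study evaluations at discontinuation, so the cross-reference could mean that visit alone, and nothing says which statement governs.

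**A reader might also infer that PFS is necessarily biased.** It is not: with stopping unrelated to progression risk, the bias in step 4 is zero. With 24 patients the simple binomial standard error near 60% is √(0.6 × 0.4 / 24) = 0.10, so the illustrated bias is at most about one standard error. This stands as a limit on the practical size, although the bias, where present, has a consistent direction and the confidence interval does not reflect it.

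**Progression after stopping is not wholly unobservable.** New anti-cancer treatment is collected, Section 13.3 counts symptomatic progression, and footnote 12 may be read as continuing CT. This is why the point is that assessment is not clearly scheduled. The start of new therapy is not a progression date, and last follow-up is undefined. If it meant last contact rather than last disease assessment, patients would count as progression-free through unassessed time, which also pushes PFS upward.

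**Toxicity does not always end treatment.** Table 2 provides for restarting after cytopenias and after Grade 3 neuropathy, so those events should not be taken as automatic exits. The neuropathy row restarts without thalidomide, which does not sit with Section 5.6; those passages must be reconciled as a separate matter. Stops without progression remain foreseeable: Table 2 removes patients for Grade 4 neuropathy and any blistering rash, and Section 5.4.1 for intolerance of either oral drug.

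**Conclusion.** The concern holds in limited form. The three follow-up statements do not agree, and none clearly schedules disease assessment after a stop without progression. The endpoint most exposed is duration of response. PFS would be overstated by about 5–10 points at 2 years if the progression hazard doubled after stopping, and not at all if stopping carried no information about progression; the rates and the doubling are assumptions. OS is estimable under the calendar and seriously overstated only under a literal 30-day reading. No decision rule uses these endpoints, and the primary response test and N = 24 are untouched. This should be fixed, but it does not threaten the trial's main conclusion.

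**What to change.** - Replace the statements in Sections 5.3 and 5.7 with one rule matching Section 10: survival and later anti-cancer treatment every 3 months for all patients until death, withdrawal or study close. Label the 28–30 days as the safety window only.
- For patients who stop without progression, record disease status at each 3-monthly contact from the routine-visit node, spleen and liver examination and blood counts, until progression or new CLL therapy. Use these data for PFS and duration of response.
- State in footnote 12 whether CT continues after treatment stops.
- In Section 13.3, give censoring rules for PFS, OS and duration of response, and define last follow-up for each.

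The cost is protocol wording plus 3-monthly abstraction for at most 24 patients at one institution. No scans or biopsies are added. One drawback should be acknowledged in the plan: progression after stopping would be found mainly by examination and counts, whereas nodal and organ response under Section 11 is judged by CT.

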### 6.2 Instructions for Initiation of a New Cycle

A new course of treatment may begin on the scheduled day 1 of a new cycle utilizing the same criteria as outlined for dose modifications in sections 6.3, table 2.

- The ANC is  $\geq 1000/\text{mm}^3$ ; if ANC is between  $500\text{-}1000/\text{mm}^3$  and not associated with fever  $\geq 38.5^\circ\text{C}$ , the new cycle should start as planned and G-CSF or pegfilgrastim may be used to support neutrophil count.
- The platelet count is  $\geq 25,000/\text{mm}^3$ ;
- Any drug-related rash that may have occurred has resolved to  $\leq$  grade 1 severity;
- Any drug-related neuropathy that may have occurred has resolved to  $\leq$  grade 2 in severity;
- Tumor lysis syndrome (TLS) has not exceeded grade 1 severity during previous cycle (see Appendix D: Cairo-Bishop Definition of Tumor Lysis Syndrome);
- If TLS  $\geq$  grade 2 during previous cycle (see Appendix D: Cairo-Bishop Definition of Tumor Lysis Syndrome), electrolyte abnormalities have resolved to  $\leq$  grade 0 severity;
- Any other drug-related adverse events that may have occurred have resolved to  $\leq$  grade 2 severity.

If these conditions are not met on Day 1 of a new cycle, the subject will be evaluated weekly and a new cycle of treatment will not be initiated until the toxicity has resolved as described above. If the dose of lenalidomide or thalidomide was reduced during the previous cycle, and the cycle was completed without requiring further dose modification, then the next cycle will start at the same doses of lenalidomide and thalidomide as given at the end of the previous cycle. **If lenalidomide or thalidomide dosing was omitted for the remainder of the previous cycle due to toxicity attributed to lenalidomide or thalidomide or if the new cycle is delayed due to lenalidomide-related or thalidomide-related toxicity newly encountered on the scheduled Day 1**, then the new cycle will be started with a one-level dose reduction of lenalidomide or thalidomide based on attribution.

## **Instructions for dose modifications or interruption**

Dose delay and dose reduction rules are as follows and in the table below.

- Lenalidomide and thalidomide dose reduction steps are outlined in Section 6.1.
- For treatment interruptions during a cycle, the 28-day schedule of each cycle will continue to be followed. Missed doses of lenalidomide or thalidomide are not made up.
- For treatment interruptions that delay the scheduled start of a new cycle, when toxicity has resolved as required to allow the start of a new cycle (Section 6.2), the restart day of therapy becomes Day 1 of the next cycle.

Dose re-escalation of lenalidomide following dose reductions due to neutropenia, thrombocytopenia, tumor lysis syndrome, tumor flare, rash, neuropathy, hypothyroidism or hyperthyroidism:

- If the dose of lenalidomide has been reduced for neutropenia, thrombocytopenia, rash, neuropathy, lenalidomide dose re-escalation is permitted if the subject completes one full cycle without experiencing any toxicity that requires dose interruption or reduction. The lenalidomide dose may be increased by one dose level at the initiation of a new cycle of therapy.
- If the dose of lenalidomide has been dose reduced for tumor lysis syndrome, lenalidomide dose re-escalation is permitted if the subject completes one full cycle without experiencing a laboratory TLS or  $\geq$  Grade 1 TLS (see Appendix D: Cairo-Bishop Definition of Tumor Lysis Syndrome), unless the subject requires a dose interruption/reduction for other toxicity.
- If the dose of lenalidomide has been dose reduced for tumor flare, lenalidomide dose re-escalation is permitted if the subject completes one full cycle without experiencing  $\geq$  Grade 1 tumor flare, unless the subject requires a dose interruption/reduction for other toxicity.
- The dose of lenalidomide will be reduced for hypothyroidism or hyperthyroidism as outlined in Table 2.
- Serum chemistry and uric acid should be closely monitored for signs of laboratory or clinical TLS (see Appendix D: Cairo-Bishop Definition of Tumor Lysis Syndrome) following lenalidomide dose re-escalation (see Section 2, Schedule of Study Assessments, for details regarding serum chemistry and uric acid monitoring).
- TLS prophylaxis with allopurinol and hydration as described in Section 5.5.1 should be considered with each dose re-escalation.

### 6.3 Instructions for dose modifications or interruption during a cycle

Table 2: Dose Modifications	
NCI CTC Toxicity Grade	Action
Grade 3 neutropenia associated with fever (temperature <math>\geq 38.5^{\circ}</math> C) or Grade 4 neutropenia	
 
• Hold lenalidomide, thalidomide and, if applicable, rituximab dosing. Omitted doses are not made up.
 
• Follow CBC weekly.
 
• Once neutropenia has resolved to <math>\leq</math> grade 3, restart treatment as scheduled. Restart lenalidomide at next lower dose level.* If neutropenia is the only toxicity for which a dose reduction is required, G-CSF or pegfilgrastim may be used in order to allow maintaining the dose of lenalidomide.
 

Thrombocytopenia <math>\geq</math> Grade 4 (platelet count <math>< 25,000/\text{mm}^3</math>)	
 
• Hold lenalidomide, thalidomide and, if applicable, rituximab dosing. Omitted doses are not made up.
 
• Hold prophylactic anti-thrombotic agents
 
• Follow CBC weekly.
 
• Once thrombocytopenia resolves to <math>\leq</math> grade 3, restart treatment as scheduled. Restart lenalidomide at next lower dose level.*
 

Platelet count <math>< 50,000/\text{mm}^3</math>	
 
• Hold prophylactic anti-coagulation, if applicable.
 
• Restart prophylactic anti-coagulation when platelet count is <math>\geq 50,000/\text{mm}^3</math>.
 

Table 2: Dose Modifications	
NCI CTC Toxicity Grade	Action

Non-blistering rash Grade 3
	
 
• If Grade 3, hold lenalidomide, thalidomide, and, if applicable, rituximab dosing. Omitted doses are not made up..
 
• Follow weekly.
 
• If rash development is related to a rituximab infusion, restart treatment as scheduled at the previous doses once toxicity resolves to <math>\leq</math> grade 1.
 
• If the development of the rash is not related to a rituximab infusion, and the rash is purpuric, vasculitic, or bullous, or possibly the result of Stevens-Johnson Syndrome or toxic epidermal necrolysis, the patient will be discontinued from the study.
 
• If the development of the rash is not related to a rituximab infusion and inconsistent with Stevens - Johnson syndrome, the clinician may re-institute therapy once the toxicity resolves to <math>\leq</math> grade 1. Re-institute lenalidomide monotherapy at a one dose level reduction. If no recurrence of the rash occurs after one week, then restart thalidomide monotherapy at 50 mg every other day. Further dose escalation of the lenalidomide will be at the discretion of the treating physician per guidelines in Section 6.2.
 

Grade 4
	
 
• Discontinue treatment and remove patient from study.
 

Desquamating (blistering) rash- any Grade
	
 
• Discontinue treatment and remove patient from study.
 

Neuropathy Grade 3
	
 
• Hold lenalidomide and, if applicable, rituximab, and discontinue thalidomide doses. Follow weekly. Omitted doses are not made up..
 
• When toxicity improves to <math>\leq</math> grade 2, restart treatment as scheduled. Restart lenalidomide one dose level lower. Thalidomide will not be re-introduced given its strong association with neuropathy.
 

Grade 4
	
 
• Discontinue lenalidomide. Remove patient from study.
 

Venous thrombosis/embolism <math>\geq</math> Grade 3
	
 
• Hold lenalidomide, thalidomide, and, if applicable, rituximab, doses and start anticoagulation; restart lenalidomide and thalidomide dosing at investigator's discretion (maintain dose level).
 
• Omitted doses are not made up..
 


Hyperthyroidism or hypothyroidism  Grade 3
	
 
• Hold thalidomide, lenalidomide and, if applicable, rituximab. Omitted doses are not made up..
 
• Evaluate etiology and initiate appropriate therapy. When toxicity improves to <math>\leq</math> grade 2, restart treatment as scheduled. Restart lenalidomide at one dose level lower and thalidomide at the same dose.
 

other non-hematologic toxicity <math>\geq</math> Grade 3
	
 
• Hold lenalidomide, thalidomide, and, if applicable, rituximab doses. Follow weekly. Omitted doses are not made up..
 
• Restart lenalidomide, thalidomide, and / or rituximab therapy at discretion of investigator, if the toxicity resolves to <math>\leq</math> grade 2 and consider dose reduction of most likely causative agent.
 

\* Lenalidomide 5 mg every 3rd even day is the minimum lenalidomide dose. Lenalidomide will be discontinued in patients who cannot tolerate this dose. However, patients who experience toxicity requiring dose reduction while receiving lenalidomide 5 mg every 3rd even day may, at the discretion of their physician, have their dose held until toxicity resolves as described in Sections 6.2 and 6.3, and then restart lenalidomide 5 mg every 3rd even day. If the same toxicity recurs at lenalidomide 5 mg every 3rd even day, consideration should be given to discontinuing lenalidomide.

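### The Table 2 restart rule for febrile Grade 3 neutropenia is already met when dosing is held and does not mention fever

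*Combined protocol and SAP*

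**What the plan says.** The neutropenia row of Table 2 in Section 6.3 has two triggers: "Grade 3 neutropenia associated with fever" (38.5 °C or higher), and Grade 4 neutropenia with or without fever. Its first bullet holds lenalidomide, thalidomide and any rituximab due. Its second asks for a weekly blood count. Its third begins "Once neutropenia has resolved to" and sets the level at Grade 3 or lower. Treatment then restarts on schedule with lenalidomide one level down, unless growth factor is used to keep the dose. No other restart condition is given.

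Four other places bear on the point:

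- **Section 6.1** tells the investigator to hold the causative agent until the adverse event resolves, and refers to Section 6.3 for the detail.
- **Section 6.2** covers Day 1 of a new cycle and says it applies the Table 2 criteria. It allows a start at an ANC of 500–1000/mm³ only when the count is low "and not associated with fever" of 38.5 °C or more.
- **The unnumbered instructions after Section 6.2** separate two cases. Interruptions that delay a new cycle follow Section 6.2. For the others: "For treatment interruptions during a cycle, the 28-day schedule of each cycle will continue to be followed".
- **The Table 2 footnote** allows patients to "have their dose held until toxicity resolves as described in Sections 6.2 and 6.3", but only when lenalidomide is already at its minimum dose.

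**The concern.** A hold-and-restart rule works only if the restart condition is false when the hold begins. For febrile Grade 3 neutropenia it is true from the start, because the patient is at Grade 3 and the bullet asks only for Grade 3 or lower. Fever is what turns this Grade 3 count into a reason to hold, yet it plays no part in ending the hold.

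At stake is a written safety rule for a toxicity that Section 2.5 names among those limiting lenalidomide. An oral agent is scheduled every day, and rituximab weekly in Cycles 1, 7, 13 and 19. Read literally, the third bullet lets these resume in a patient who is still febrile and neutropenic, while the first forbids it. The only follow-up the row names is a weekly blood count, which does not record temperature.

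**Working it through.** The plan gives no figure to reproduce here. The check is a logical one, comparing each trigger with its own restart condition.

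**Step 1. States.** Take three grade bands (Grade 4, Grade 3, Grade 2 or lower), each with or without fever of at least 38.5 °C: 3 × 2 = 6 states. To place Section 6.2 on the same grid, assume that an ANC of 500–1000/mm³ is Grade 3 and 1000/mm³ or more is Grade 2 or lower. The CTCAE cut-offs are not printed in the protocol. Both sections use the same 38.5 °C limit.

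| State | Hold trigger met | Printed restart met | Amended restart met | Section 6.2 neutrophil bullet allows start |
|---|---|---|---|---|
| Grade 4, febrile | yes | no | no | no |
| Grade 4, afebrile | yes | no | no | no |
| Grade 3, febrile | yes | **yes** | no | no |
| Grade 3, afebrile | no | yes | yes | yes |
| ≤ Grade 2, febrile | no | yes | yes | yes |
| ≤ Grade 2, afebrile | no | yes | yes | yes |
| **Total yes** | 3 | 4 | 3 | 3 |

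**Step 2. Conflicts.** Every state is covered by at least one rule, so overlap = holds + restarts − 6.

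- As printed: 3 + 4 − 6 = 1, which is febrile Grade 3.
- With the amended restart (Grade 2 or lower, or Grade 3 without fever): 3 + 3 − 6 = 0, and no state is left without a rule.

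**Step 3. Agreement with Section 6.2.** The printed restart agrees in 5 of 6 states and differs at febrile Grade 3. The amended restart agrees in 6 of 6. This is expected, since it borrows the Section 6.2 limit. It shows that the repair adds no new standard.

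**Step 4. The other rows of Table 2 with a graded restart of study drug.**

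| Row | Trigger grade | Restart grade |
|---|---|---|
| Thrombocytopenia ("Once thrombocytopenia resolves to") | 4 | ≤ 3 |
| Non-blistering rash | 3 | ≤ 1 |
| Neuropathy (lenalidomide only) | 3 | ≤ 2 |
| Thyroid | 3 | ≤ 2 |
| Other non-hematologic ("therapy at discretion of investigator, if the toxicity resolves to") | ≥ 3 | ≤ 2 |

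All 5 restart below the trigger grade. The neutropenia row does so for 1 of its 2 triggers. Venous thrombosis restarts at the investigator's discretion and is not counted. The row for platelets below 50,000/mm³ governs anticoagulation, not study drug.

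**Step 5. Does other text close the gap?** Section 6.1 hands the detail back to Section 6.3, which contains the row in question. Section 6.2 governs Day 1, and the instructions that follow it extend its conditions only to interruptions that delay a cycle. The footnote is confined to the minimum lenalidomide dose. An accompanying non-hematologic toxicity of Grade 3 or higher would trigger its own hold. What remains is the mid-cycle patient, still febrile at Grade 3, with no other Grade 3 toxicity.

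**The case against.** The best reply is that the row settles the matter itself. The trigger describes a state, so a patient restarted while still febrile at Grade 3 would meet it again at once. The word resolved implies improvement, and only the hold reading gives the febrile Grade 3 trigger any effect. Section 6.1 points the same way. Section 6.2 claims to use the Table 2 criteria and then spells them out with a fever condition, which is evidence of what Table 2 means even if Section 6.2 applies only on Day 1.

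Much of this stands. The hold reading is very likely the intent, and most clinicians would wait. On that reading the hold does have an end, when either the fever or the Grade 3 neutropenia resolves. But that end is nowhere written for a restart within a cycle, and the target that is written equals the trigger grade. A safety rule should not depend on the reader setting aside one of its own bullets.

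The comparison with the other rows also has a limit. Those triggers depend on grade alone, whereas this one can also end when fever clears, and Section 6.2 shows that treating at afebrile Grade 3 is deliberate. So the Grade 3 threshold is not itself the error; the missing fever clause is. It is fair, too, that one state in six is not a frequency, and that the situation is narrow in a 24-patient, single-institution study.

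**Conclusion.** The concern holds. As printed, the row gives contradictory instructions in one of six states: febrile Grade 3 neutropenia during a cycle. This is an error in a patient-safety rule and should be corrected, although its scope is small.

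The conflict follows from the printed text alone. Only the comparison with Section 6.2 needs the assumed grade cut-offs. The documents give neither the frequency of febrile Grade 3 neutropenia nor the length of the fever, so no number of patients or doses can be attached. The weekly blood count, the default lenalidomide reduction, and the investigator's authority under Section 5.6 to stop treatment all remain as safeguards. There is no consequence for the primary endpoint, sample size or two-stage rule.

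**What to change.** In the third bullet of the neutropenia row, replace the restart level with: *≤ grade 2, or grade 3 not associated with fever ≥ 38.5 °C*. Leave the weekly blood count, the dose reduction and the growth-factor option as they are.

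The fever condition should attach to Grade 3 only. Section 6.2 lets a patient with an ANC of 1000/mm³ or more start whatever the temperature, and the amended bullet keeps that. The wording also keeps on hold a Grade 4 patient who recovers only to febrile Grade 3. Under the hold reading this changes nothing, because that patient already meets the trigger. Under the literal restart reading it lengthens some holds slightly, which is the only clinical cost.

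The change is one phrase in one table cell, made by amendment. Sample size, alpha, power and visit schedule are unchanged.
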